According to National TB Program data, in 2018 2200 persons were started on TB treatment and 45% among them were ≤ 15 years old.

MSF OCBA launched the permanent mission in Guinea Bissau (figure 2) in 2016 as a strategic choice with the objective to test and develop innovative medical strategies in paediatric care to decrease childhood mortality and which will ultimately help to overcome operational challenges, by being capitalized and exported to more unstable settings. MSF supports several departments in the Simão Mendes National Hospital in collaboration with MoH: paediatric intensive care unit (PICU), neonatal intensive care (NICU), in-patient therapeutic feeding centre (ITFC) and few beds in the paediatric ward. MSF is currently diagnosing TB in children and referring them to MoH / National TB program to initiate and continue treatment.

Figure 2:

6. Objectives

a. Main objective

To determine the sensitivity and specificity of Xpert MTB/RIF Ultra in stool and urine samples in suspected paediatric TB cases in comparison with the WHO recommended test (Xpert MTB/RIF Ultra in sputum sample or validated extrapulmonary sample).

b. Secondary objective

- 1) To determine the sensitivity and specificity of Xpert MTB/RIF Ultra rifampicin resistance using stools and urine in pulmonary and extra pulmonary TB confirmed and unconfirmed TB cases as a composite.
- 2) To disaggregate according to HIV status (positive, negative) and to nutritional status (SAM or not).
- 3) Describe the prevalence of positive TB LAM in HIV-infected, HIV-uninfected and SAM patients with and without TB.

7. Patients and Methodology

a. Study design

We plan to conduct a multicentric study in 2 different centres: Malakal (South Sudan) and Bissau (Guinea Bissau). The methodology for the evaluation of Xpert MTB/RIF Ultra in stools and urine will be a cross-sectional study.

b. Study sites

This study will be conducted in South Sudan in two different sites, the Malakal POC and the Malakal town, and in Bissau in one site, the Simão Mendes National Hospital.

c. Partnership and study coordination

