In South Sudan, this study will be conducted in partnership between Médecins sans Frontières Operational Centre Barcelona-Athens (OCBA) and the Ministry of Health of South Sudan, in collaboration with the National TB Program. The MoH is willing to provide administrative and political support. The Xpert MTB/RIF Ultra machine was procured by MoH as well. No academic institutions have been involved in the study.

In Guinea Bissau, this study will be conducted in partnership between MSF OCBA and the MoH of Guinea Bissau, in close collaboration with the National TB Program. MSF works closely with MoH in Simão Mendes hospital, and the General Director of the TB hospital (Raoul Follereau Hospital), as well as the Responsible of the TB ambulatory care at Simão Mendes, are co-authors of the study and willing to provide technical support.

d. Study participants and sample size

1. Research population

The research population are children with presumptive TB in (Malakal town and POC hospitals) or in Bissau (Simão Mendes National Hospital).

Note that the same population will be offered to participate in the study “Evaluation of point of care ultrasound (POCUS) for the diagnosis of TB in children” (ref: MSF ERB 18116) which will be submitted in a separate protocol. Note that all participants will be asked to sign 2 separate consent forms.

2. Participants: inclusion criteria

- Any child from 6 months of life to 15 years old
- TB suspected according to diagnostic criteria
- Informed consent provided by legal responsible or companion

3. Participants: exclusion criteria

- Patients who have received TB treatment for > 1 day in the last 3 months
- Patients not producing stools during period of hospitalization

4. Sample size

The primary analysis will be to describe the performance of Xpert MTB/RIF Ultra from stools and urine in patients with confirmed TB. The estimated total sample size is **327 suspected TB patients: 143 in Malakal and 184 in Bissau**. The sample size difference is justified by the number of suspected patients currently consulted in both settings. Note that this is the same sample size

that will be used for the study “Evaluation of point of care ultrasound (POCUS) for the diagnosis of TB in children”.

The sample size has been estimated with a variety of assumptions: we assume that sensitivity of Xpert MTB/RR in stools and urine will be 60% and specificity 95%.

Expected sensitivity	Precision			
	0.05	0.07	0.1	0.12
0.5	385	196	97	67

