0.6	369	189	93	64
0.7	323	165	81	56

With a precision of 12%, total number of 64 patients will be required to have a diagnosis of confirmed TB. If we assume that positivity of Xpert MTB/RR in sputum or validated extra pulmonary sample will be 20% (rate non-sick/sick = 4), we will need a total of 320 suspected TB patients will be needed (160 per project) to achieve 64 patients with confirmed TB (32 per project). We assume that 2% of the children won't be capable of producing stools, therefore the final sample size will be 327.

e. Definitions

1. SAM (severe acute malnutrition) in children:

- Children < 5 years old: Z-score weight / height <-3 and / or MUAC <11.5 cm, and / or bilateral oedema.
- Children 5-15 years old: weight for height < 70% (see table in Appendix 16) or bilateral oedema

2. HIV infection:

All patients with suspected TB will be tested for HIV, after consent of the legal responsible and pre-test counselling. The algorithm test will be adjusted to the age of the child (see Appendix 12). All children < 18 months will need PCR DNA for HIV diagnosis. All children ≥ 18 months and > 6 weeks of breastfeeding cessation will follow same diagnostic algorithm as for adults, which requires 3 positive rapid tests.

3. Suspected case of tuberculosis (40,41):

Any child with at least one of the following signs, symptoms or features is considered a **suspected case of tuberculosis** (Appendix 4):

- Persistent cough for more than 2 weeks
- Unexplained fever for more than a week
- Suspected extra-pulmonary tuberculosis (TBEP), e.g.:
 - Angular deformation of the spine (gibbous)
 - Lymphadenopathy
 - Subacute meningitis
 - Abdomen distended with ascites

- > 2 weeks of diarrhoea
- Painless enlarged joints
- Pleural effusion
- Other

All **HIV positive** and **SAM children**, as well as all **TB contacts**, will systematically and actively be screened for TB.

Tuberculosis screening in children is done on admission and during hospitalization. If children are not identified as suspected TB cases at admission, a new assessment will be done after 1 week of admission. In addition to the above criteria, tuberculosis is suspected based on the following signs, symptoms and characteristics during hospitalization:

- Low weight gain despite correct nutritional treatment
- Persistent pneumonia after adequate and well-followed antibiotic therapy
- Persistence of cough

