- Persistent fever ($>38^{\circ}\text{C}$) beyond one week after exclusion from classical causes such as malaria or pneumonia
- Persistence or aggravation of fatigue
- Chest radiographs imaging suggestive of tuberculosis

4. Case with diagnosis of tuberculosis (40,41)

- **Confirmed TB:** patients with Xpert MTB/RIF Ultra positive (or TB culture positive when available) in a respiratory sample (pulmonary TB) or in other sample, such as CSF, lymph node or other tissue/liquid (extra pulmonary TB); TB LAM positive in HIV-infected patients.
- **Unconfirmed TB:** no microbiological confirmation but clinical diagnosis of TB and started on anti TB treatment (as established in Appendix 5).
- **Unlikely TB:** good response to other treatments (antibiotic, nutritional support, etc.) and no suggestive symptoms after 1 week of admission and until the 2 month follow-up.

8. Study procedures

a. Identification of participants

Eligible children will be identified upon admission to paediatric ward, ITFC, PICU/NICU (in Bissau) or as suggestive cases in OPD. The identification of suspected TB cases will be mainly based on clinical criteria. A diagnostic algorithm (Appendix 4) will be applied to all suspected cases. The populations of interest for this study are hospitalized children, severely malnourished (SAM) and HIV positive or exposed children.

b. Laboratory

1. Sample collection

All patients included in the study will have requested one stool and one urine sample. The team will follow a specific SOP for respiratory sample collection (naso-pharyngeal aspirate, gastric lavage or spontaneous sputum), stools, urine and lymph nodes (or other validated extra pulmonary samples) as described in the appendixes. In hospitalized children, all samples will be collected during hospitalisation and patients not capable of producing the required sample (stools/urine) during this period will be excluded from the study. For ambulatory patients, samples will be collected within 2 hours and, if child not capable of producing stools/urine, samples will be requested to be brought by parents or guardians the day after.

2. Laboratory procedures

Xpert MTB/RIF Ultra will be performed to respiratory or extra pulmonary validated samples, stools and urine for all patients at baseline, and for those with negative results and persistent symptoms, will be repeated after 1 to 2 weeks.

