- Consent to be traced in case of defaulting

2. CLINICAL AND DIAGNOSTIC INFORMATION OF STUDY PARTICIPANTS AT BASELINE:

[figure not shown]
- Entry point (OPD, TB or HIV or Nutrition program, IPD)
- History of TB contact, HIV or malnutrition
- Temperature (axillary) (°C)
- Weight and size
- Nutritional status
- Co-morbidities: malaria, respiratory infection, HIV status
- Signs and clinical symptoms suggestive of tuberculosis
- Final diagnosis
- TB treatment started: Yes / No
- Date of TB treatment started

[figure not shown]
3. LAB EXAMS INFORMATION:

- Program identification number
- Inclusion number in the study
- Date of respiratory sample collection
- Type of procedure: spontaneous sputum, naso-pharyngeal aspirate, gastric aspiration
- Date of Xpert MTB/RIF Ultra in respiratory sample performed (1 sample)
- Result of Xpert MTB/RIF Ultra (negative, positive RIF resistance negative, positive RIF resistance positive, indeterminate)
- Date of stools collection
- Date of Xpert MTB/RIF Ultra in stools performed (1 or 2 samples)
- Result of Xpert MTB/RIF Ultra (negative, positive RIF resistance negative, positive RIF resistance positive, indeterminate)
- Date of urine collection
- Date of Xpert MTB/RIF Ultra in urine performed (1 or 2 samples)
- Result of Xpert MTB/RIF Ultra (negative, positive RIF resistance negative, positive RIF resistance positive, indeterminate)

e. Flow of patients

OPD patients who don't need hospitalization will be requested to stay in observation for 2 hours to perform all exams after obtaining the informed consent. If the participant is not able to produce stools within this time, s/he will be requested to bring the sample once produced at home (all information in Appendix 3). Please, find the flow in the following page.

9. Safety Considerations

There are safety considerations related to infection control of TB, even if children are only considered contagious after they acquire the capacity of expectorating (> 8 years old). For older children, isolation procedures for coughing patients, as well as protection measures for medical staff, need to be implemented. Lab staff needs to wear respirator and gloves when manipulating samples for Xpert MTB/RIF Ultra. Safety procedures related to Xpert MTB/RIF Ultra need to be in place.

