Diagnostic procedures are routinely done in all children with suspected TB (not specifically for the study). Gastric lavage and naso-pharyngeal aspirate can be uncomfortable. For gastric lavage, there's a small risk of spasms of vocal cords, tube entering in the airway instead of the oesophagus, minor bleeding or aspiration pneumonia. Regarding naso-pharyngeal aspirate, the actual risks for participants are still smaller; it can cause nausea or local annoyance. Lymph node puncture is a routine procedure as well and is only performed in palpable lymph nodes (≥ 2 cm). The risks are small and can comprise blood vessel puncture or accidental exposure to blood for the staff. All three are common procedures which will only be performed by trained staff. Any possible complication will be treated by MSF.

Collection of stool and urine specimens poses no risk. Since individual risks to children are small, reporting of adverse events and setting up of an external data safety monitoring board are not considered necessary for this study.

10. Data Management and Analysis

The number of children screened by the program for suspected tuberculosis, the number of eligible children and the number of cases included in the study during the recruitment period will be noted. The number of parents or guardians of eligible children who refuse their participation will also be registered. Demographic, clinical and diagnostic characteristics at baseline and during patient follow-up under the program will also be recorded.

This information will be used to describe the characteristics of the patient population included, and will allow comparison of the characteristics of patients with positive Xpert in stools and urine in comparison with those who test negative. The main outcome of interest for the Xpert MTB/RIF Ultra study is establishing the sensitivity and specificity for Xpert in stools and urine (compared with gold standard).

Data will be collected in the files by the study team members. Data will be coded and entered into RedCap database, and analysed with SPSS statistical software. Continuous variables (e.g.

age, distance) will be summarized using mean and standard deviation or median and interquartile range as appropriate and may also be expressed as ordinal categories with frequencies; frequencies will be reported with corresponding 95% confidence intervals.

11. Ethical Considerations

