All information collected during the study will be recorded and identified by a specifically assigned number for the study and the number assigned routinely for the program. Patient or parent or guardian names will not be recorded in the study form or electronic databases. Access to the study information (in paper or electronic format) is restricted to authorized staff.

Informed consent forms will be kept in a secure and confidential place in a locked cabinet by the study coordinator throughout the study. The consent forms will be archived for a minimum of 5 years after the end of the research, in a secure and locked archive by the investigator at MSF OCBA, in Barcelona. After this period, all documents will be destroyed. If the Ministry of Health requests to archive copies of the informed consents, they will be given at the end of the research study.

c. Benefits

We expect that the study will validate the use of Xpert MTB/RIF Ultra in stools and urine for pediatric TB diagnosis. Improved tools for paediatric TB diagnostic will ultimately have an impact in reducing mortality in children with TB disease. We expect that the results of the study will build the base of an improved diagnostic strategy in which diagnostic tools are more adapted to a particular operational/epidemiological context.

At an individual level, a potential benefit would be a most efficient diagnosis of TB in the child, which will lead to an earlier treatment and improved prognosis. All patients will be included in the TB (and HIV when required) program. The community will benefit of the improved TB detection in children.

d. Risks

The potential risk for the implementation related to the study is eventual challenges in availability and implementation of new tools and consumables (Xpert MTB/RIF Ultra). The risks linked to the field might be instability of the context and lower recruitment rate than expected which would lead to a longer duration of the study.

Regarding the potential individual risks for the subjects in the study could be a longer stay at the hospital. The risks related to sample collection are described in section 9 and can be related to gastric lavage, naso-pharyngeal aspirate or lymph node puncture; these procedures are used routinely for the diagnosis and not specifically for this study. No harms are expected in stools or urine collection.

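### The two inpatient exclusion rules disagree (no stool in 7.d.3, stool/urine in 8.b.1), and excluding a child for one missing specimen discards a usable result for the other; the effect is small and the fix cheap

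*Combined protocol and SAP*

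**What the plan says.** The main objective (6.a) covers both index tests: "sensitivity and specificity of Xpert MTB/RIF Ultra in stool and urine samples in suspected paediatric TB cases", each against Ultra on sputum or a validated extrapulmonary sample. Section 8.b.1 asks for both specimens from every child: "All patients included in the study will have requested one stool and one urine sample".

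The rules for a missing specimen are:

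- **7.d.3, exclusion criteria:** "Patients not producing stools during period of hospitalization". Urine is not mentioned.
- **8.b.1, hospitalised children:** "patients not capable of producing the required sample (stools/urine) during this period will be excluded from the study".
- **8.b.1, ambulatory children:** a missing sample is to be brought the following day. No exclusion is stated if it never arrives.

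The sample size (7.d.4) allows 2% for children who will not "be capable of producing stools, therefore the final sample size will be 327". It makes no allowance for missing urine, although the 60% sensitivity and 95% specificity are assumed for both specimens. Section 10 defines no analysis set and gives no rule for a child with only one specimen.

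**The concern.** An eligibility rule written in two ways can be applied differently by two members of staff, each following the protocol.

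The exclusion also appears to serve no analytic purpose. The stool 2x2 table needs a stool result and a reference result; the urine table needs a urine result and a reference result. Removing a child from both because one specimen is missing discards a valid pair.

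What is lost depends on whether excluded children are replaced, which the text does not say. Section 11.d mentions "lower recruitment rate than expected which would lead to a longer duration of the study", which may mean recruiting to target. Without replacement the cost is precision; with replacement it is extra recruitment.

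There is also a reporting gap. For children who stay in the study, missing specimens can be counted from the lab CRF (Appendix 17) together with the entry point recorded under 8.d.2. Section 10 counts children screened, "the number of eligible children and the number of cases included in the study", and refusals. It does not list children excluded for a missing specimen, or which specimen they lacked. For a study meant to support routine stool and urine testing, that number matters in itself.

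**Working it through.** **1. The two rules side by side.**

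| Inpatient gives | 7.d.3 | 8.b.1, slash = either missing | 8.b.1, slash = both missing |
|---|---|---|---|
| urine, no stool | excluded | excluded | kept |
| stool, no urine | kept | excluded | kept |

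On the either reading the rules conflict in the second row; on the both reading, in the first. The either reading is likelier, because the same paragraph requests both specimens from every child. On both readings 7.d.3 removes the child with urine but no stool.

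**2. The plan's own figures (7.d.4).** Inputs: sensitivity 0.60, precision 0.12, reference-positive rate 20%, no-stool rate 2%; 95% confidence from section 10.

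- Confirmed cases: 1.96² × 0.60 × 0.40 / 0.12² = 64.03 (stated: 64)
- Suspected cases: 64 / 0.20 = 320
- Inflated: 320 / 0.98 = 326.5, so 327

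All three reproduce. Expected with stool: 327 × 0.98 × 0.20 = 64.09 confirmed and 327 × 0.98 × 0.80 = 256.4 not confirmed.

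**3. Loss from 7.d.3, any reading.** At most 327 × 0.02 = 6.54 urine pairs: 1.31 confirmed and 5.23 not.

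**4. Further loss if 8.b.1 means either, no replacement.** The urine failure rate u is assumed, because the documents give none. It is taken as independent of TB status and of stool failure and applied to all children. The exclusion is written for inpatients only, so these are upper bounds.

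- Confirmed cases kept: n = 64.09 × (1 − u)
- Sensitivity half-width: 1.96 × √(0.24 / n)
- Specificity half-width: 1.96 × √(0.0475 / (256.4 × (1 − u)))

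| u (assumed) | Confirmed with stool | Sensitivity half-width, points | Specificity half-width, points |
|---|---|---|---|
| 0 | 64.1 | 12.0 | 2.7 |
| 2% | 62.8 | 12.1 | 2.7 |
| 5% | 60.9 | 12.3 | 2.7 |
| 10% | 57.7 | 12.6 | 2.8 |
| 20% | 51.3 | 13.4 | 3.0 |

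For scale, the chance SD of the confirmed count is √(320.5 × 0.2 × 0.8) = 7.2. The loss at u = 10% is 64.1 − 57.7 = 6.4 cases, which is less than that.

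**5. With replacement.** Children needed for 320 with both specimens: 320 / (0.98 × (1 − u)) = 333.2, 343.7 and 362.8 at u = 2, 5 and 10%. Rounded up, that is 334, 344 and 363 instead of 327, again upper bounds.

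**6. Under per-specimen sets, N = 327.** Stool keeps 64.1 confirmed pairs and 12.0 points whatever u is. Urine has 327 × 0.20 × (1 − u) confirmed pairs:

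| u (assumed) | Urine pairs, per-specimen | Half-width | Urine pairs, no-stool children also dropped | Half-width |
|---|---|---|---|---|
| 2% | 64.1 | 12.0 | 62.8 | 12.1 |
| 5% | 62.1 | 12.2 | 60.9 | 12.3 |
| 10% | 58.9 | 12.5 | 57.7 | 12.6 |

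**The case against.** The strongest reply is that the only loss resting on a figure in the plan is already budgeted. After 2% are dropped for no stool, 64.1 confirmed cases remain, which is the planned 64. The urine pairs lost through 7.d.3 are therefore surplus to target, and recovering them improves the urine margin by only about 0.1 point. Anything larger needs both the either reading and a urine failure rate that the documents do not give; inpatients have the whole stay to produce urine. This is right, and it limits the point to a small one.

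A set of children with both specimens does give a like-for-like comparison of stool and urine on one denominator. It can be reported as a subset without excluding anyone, so it does not justify the rule.

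Section 10's counts may capture these exclusions in aggregate, as eligible minus included minus refused, if exclusion follows eligibility. The specimen that was missing would still be unknown.

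The patient-flow figure announced in 8.e and the caretaker sheet (Appendix 3) are not in the text available here. The statement that replacement is not addressed applies only to the text that can be read.

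Finally, the summary's timeframe ends in July 2021, while 8.b.2 starts LAM testing in November 2021. This version may therefore be a late one, and an amendment cannot bring back children already excluded. That limits the gain, but the rules still need reconciling.

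**Conclusion.** The concern holds. Sections 7.d.3 and 8.b.1 give different exclusion rules on either reading of the slash, and nothing in the available text reconciles them. On any reading, a valid pair for one primary index test is discarded because the specimen for the other is missing.

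The effect on precision is small: about 0.1 point of the urine margin at the plan's 2% no-stool rate. On the either reading it reaches up to 0.6 point of the stool margin at an assumed 10% urine failure, and up to 1.4 points at an assumed 20%. These figures rest on the stated independence assumptions.

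They cover precision only. Children who cannot give a specimen may differ clinically from those who can, and the documents do not allow any resulting bias to be sized. The change is worth making because the contradiction is real and the remedy cheap; the study's conclusions are not in jeopardy.

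**What to change.** - Reconcile 7.d.3, 7.d.4 and 8.b.1 into one rule. Do not exclude an enrolled child who lacks only one of the two specimens. State the rule for ambulatory children whose sample never arrives.
- In section 10, define two analysis sets: stool in all children with a stool and a reference result, and urine in all children with a urine and a reference result. Children with both can be reported as a subset for direct comparison.
- Record and report how many children could not give each specimen, by site and by inpatient or outpatient.
- State in 7.d.4 that 12-point precision at N = 327 allows for missing stool only, and that urine precision depends on urine yield.

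**Cost:** no new patients or tests. It needs a minor amendment, because 7.d.3 is an eligibility criterion and the protocol goes to ethics committees (section 11), and one field per specimen for a sample not obtained. The drawbacks are slightly different denominators for stool and urine, and no recovery of urine precision if many children give no urine.

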Xpert MTB/RIF for stools has also been considered in several studies (21-26) but its use is not yet recommended by the WHO. The sensitivity of the stool Xpert ranged between 45 and 83%, which suggests that it is a potential alternative screening test for children with suspected TB when sputum is unavailable. In one of the studies (21), stool Xpert could rapidly confirm TB in children who present with radiologic findings suggestive of severe TB.

The main challenge is confirming TB diagnosis with the gold standard – TB culture. Thus, many of the studies had very few patients (all of them < 75 children). However, the evidence suggests that stools, which are easily obtainable, are an appropriate alternative sample for the diagnosis of pulmonary TB, especially for children unable to give respiratory samples. This is true for both HIV positive and negative individuals. “Valid specimens” for the detection of DNA of *M. tuberculosis* with Xpert include respiratory specimens from sputum sampled by expectoration, sputum induction, gastric aspirates, or nasopharyngeal aspirates and can include the use of a stool sample (19,20).

Urine Xpert has produced less interest among clinicians. Of the few studies (27,28,29), all of them focus on adult HIV+ patients. As main conclusions, urine-based MTB/RIF, alone or in combination with LAM antigen detection and/or sputum Xpert MTB/RIF, may potentially aid the

diagnosis of TB in HIV-infected patients with advanced immunosuppression when sputum-based diagnosis is not possible. Further studies are necessary to assess the utility of urine Xpert MTB/RIF in the diagnosis of TB in children.

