TB LAM in urine will be tested in all Malakal patients (starting from November 2021) and the result (negative/positive and grade 1-4) recorded in the CRF Lab form. The result will be shared with Research Manager who will only communicate to clinicians in case of HIV-infected patient; in these patients, TB LAM will be used as per clinical protocol.

3. Sample handling and storage

Respiratory specimens will be collected at the clinic and samples will be kept between 2 and 8°C until processed. Processing will be done within the 24 hours and not more than 72 hours after collection. A sterile stool container and instructions will be provided to the parent or guardian for specimen collection and handling. Following delivery to the laboratory, the stool specimen will be kept in a cool dry place and processed within 2 hours. Samples obtained in this study will adhere to all local laboratory procedures governing the storage of biological specimens.

c. Linkage to care for HIV/TB patients

All patients HIV positive will be enrolled into **HIV care** either in MSF program (Malakal) or MoH programs (Bissau). MSF will guarantee that all children will be started on ART after 2 weeks of TB treatment (or as soon as possible if TB has been excluded) or differed to 4-6 weeks in case of TB meningitis.

All TB cases (confirmed or unconfirmed) will be enrolled in **TB care** in MSF program (Malakal) or MoH program (Bissau). MSF will ensure all patients to be started on adequate weight-based dose fix combinations and followed up during the length of treatment. All children diagnosed of DRTB will be initiated on DRTB treatment regimen according to national recommendation.

In patients where stool samples yield positive results and sputum tests are negative, stool results will be communicated to Study Coordinator on site for interpretation and appropriate clinical management. Where stools results are concordant with sputum results, no additional information will be provided.

As a transversal study, it is not foreseen to follow-up patients for study purposes. The follow-up will be required though for the study “Evaluating POCUS to improve TB diagnosis in children”.

d. Data collection

The following information will be noted in an individual case study report form (CRF) for each participant:

1. DEMOGRAPHIC INFORMATION AND INFORMED CONSENT OF PATIENTS:

- Study code
- Date of birth / age
- Sex
- Parent or guardian's informed consent: Yes / No

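### The reference standard is worded inconsistently: confirmed TB in 7.e.4 is wider than the 6.a reference and does not shut out urine, and the composite in secondary objective 1 cannot work as written

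*Combined protocol and SAP*

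**What the plan says.** **Primary reference.** Section 6.a compares stool and urine with "Xpert MTB/RIF Ultra in sputum sample or validated extrapulmonary sample". The summary gives the comparator as a gold standard, Xpert Ultra, without naming a specimen. Section 10 says only gold standard.

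**Sample size (7.d.4).** "The primary analysis will be to describe the performance of Xpert MTB/RIF Ultra from stools and urine in patients with confirmed TB". The same section then applies a 20% positivity rate for sputum or validated extrapulmonary Xpert to reach 64 confirmed cases.

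**Case definitions (7.e.4).** Confirmed TB covers Xpert Ultra or, when available, culture in a respiratory sample, "or in other sample, such as CSF, lymph node or other tissue/liquid (extra pulmonary TB", and also a positive TB LAM in HIV-infected patients. Unconfirmed TB is "no microbiological confirmation but clinical diagnosis of TB and started on anti TB treatment", by reference to Appendix 5.

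**Composite.** Secondary objective 1 (6.b) concerns "Xpert MTB/RIF Ultra rifampicin resistance using stools and urine in pulmonary and extra pulmonary TB confirmed and unconfirmed TB cases as a composite".

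**Release of results (8.c).** When stool is positive and sputum negative, "stool results will be communicated to Study Coordinator on site for interpretation and appropriate clinical management". Concordant stool results are not passed on.

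**Repeat testing (8.b.2).** Xpert, "for those with negative results and persistent symptoms, will be repeated after 1 to 2 weeks".

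**The concern.** There are two separate problems.

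**Which reference builds the primary table.** An analyst who follows 6.a and one who follows 7.d.4 with 7.e.4 will not classify the same children as reference-positive. The second label adds culture and LAM, drops the requirement that the extrapulmonary sample be validated, and does not exclude the index specimens. Section 8.b.2 plans LAM only for Malakal patients, from November 2021, so that label would also differ by site and period. The discharge diagnosis on the clinical CRF (Appendix 4) has boxes for confirmed TB with no limit on the confirming specimen, so the wider label is easy to pick up by accident.

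**What the composite is for.** As worded, it concerns rifampicin resistance. Appendix 12 says that a rifampicin result exists only when MTB is detected, and unconfirmed children have no microbiological confirmation, so they have no reference result. If the composite were used for TB detection instead, the children whose stool results are released under 8.c could become unconfirmed TB through treatment start. They would then move from false positive to true positive because of the test under evaluation. That raises sensitivity and specificity together, in the direction the study expects. Section 10 says nothing about these children.

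**Working it through.** **The plan's own figures.** With expected sensitivity 60% and precision 12%: 1.96² × 0.60 × 0.40 / 0.12² = 64.03, stated as 64. Then 64 / 0.20 = 320, and 320 / 0.98 = 326.5, stated as 327. All reproduce, and nothing below changes them.

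**Planning 2×2 table (7.d.4: 64 reference-positive, 256 reference-negative, 60% and 95%).** True positives 64 × 0.60 = 38.4; false negatives 25.6; false positives 256 × 0.05 = 12.8; true negatives 243.2. So about 13 reference-negative children would be index-positive.

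**Primary table if urine Xpert counted as confirming (the literal 7.e.4 reading).**
- Urine as index: sensitivity (38.4 + 12.8) / (64 + 12.8) = 66.7%; specificity 100% by construction. Under 6.a: 60% and 95%.
- Stool as index, no overlap between the stool-positive and urine-positive reference-negatives: 38.4 / 76.8 = 50.0% and (243.2 − 12.8) / 243.2 = 94.7%. With full overlap: 66.7% and 100%.

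**Rifampicin reading.** Section 5 gives MDR in new cases as 3% (South Sudan) and 2.5% (Guinea Bissau). Taking these as rifampicin resistance, with 32 confirmed per project: 32 × 0.03 + 32 × 0.025 = 1.76 resistant children. At 60% stool detection, 1.76 × 0.60 = 1.06 would have a stool result.

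**Composite used for TB detection.** Three inputs are assumptions, because the documents give none of them: U, the unconfirmed cases called without help from stool; p, the share of U that is stool-positive; and f, the share of the remaining discordant children called TB because of the stool result. Let k = Up, d = 12.8 − k and m = fd. Then

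sensitivity = (38.4 + k + m) / (64 + U + m)

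specificity = (256 − U − d) / (256 − U − m)

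For U = 64 and p = 10%, k = d = 6.4:
- f = 0: 44.8/128 = 35.0%; 185.6/192 = 96.7%
- f = 0.25: 46.4/129.6 = 35.8%; 185.6/190.4 = 97.5%
- f = 0.5: 48/131.2 = 36.6%; 185.6/188.8 = 98.3%
- f = 1: 51.2/134.4 = 38.1%; 100%

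Specificity shift at f = 0.5, in points, with the 95% half-width at f = 0:

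| U | p | shift | half-width |
|---|---|---|---|
| 32 | 5% | 2.4 | 2.9 |
| 32 | 10% | 2.1 | 2.7 |
| 64 | 5% | 2.4 | 3.1 |
| 64 | 10% | 1.6 | 2.5 |
| 64 | 20% | 0 | – |
| 96 | 5% | 2.4 | 3.4 |
| 96 | 10% | 1.0 | 2.2 |

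At U = 64 and p = 20%, k = 12.8 and d = 0, so no discordant child remains to be moved, whatever f is. At p = 5%, stool is positive in unconfirmed TB no more often than in reference-negative children overall; a lower p would give a larger shift. For U of 32 to 96 and p of 5% to 10%, the sensitivity shift at f = 0.5 is 0.7 to 3.2 points, against half-widths of 6.9 to 9.9.

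**Do bounds capture it?** Take U = 64, p = 10%, f = 0.5. The stool-positive, reference-negative, treated children number k + m = 9.6.
- Counted as TB: 36.6% and 98.3%.
- Counted as not TB: 38.4/121.6 = 31.6% and 185.6/198.4 = 93.5%.
- Excluded: 31.6% and 98.3%.

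The unbiased 35.0% and 96.7% lies between the first two. Exclusion is not neutral.

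**The case against.** The strongest defence is that the primary reference is in fact settled. Section 6.a names it, and 7.d.4 itself derives the 64 confirmed cases from sputum or validated extrapulmonary positivity. The lab CRF (Appendix 17) records each specimen separately, so a clean table can be built. This largely stands. What remains is that 7.d.4, 7.e.4 and section 10 are not tied back to 6.a.

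A reader might infer that a positive stool confirms TB, so that stool specificity is 100% by construction. The background does say that valid specimens "gastric aspirates, or nasopharyngeal aspirates and can include the use of a stool sample". But that is literature review, and it also notes that WHO does not yet recommend stool Xpert. The open clause in 7.e.4 concerns extrapulmonary TB; 8.b.2 and the lab CRF list stool and urine apart from validated samples; and sending discordant stool results for interpretation would be pointless if stool confirmed TB. Reading stool into 7.e.4 is strained. Only urine fits the word liquid literally, and the separate listing in 8.b.2 and the CRF counts against that too.

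A reader might also infer that the study plans TB-detection accuracy against confirmed plus unconfirmed TB. It does not say so: the composite appears only for rifampicin resistance, so the incorporation argument is conditional.

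Three further limits stand. Release is for interpretation and is not an automatic diagnosis. Some discordant children may become reference-positive legitimately on repeat testing. Unconfirmed TB is defined through Appendix 5, whose flowchart is not shown in the text available, so how a positive stool or urine result feeds that diagnosis is not fully visible.

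**Conclusion.** The point holds as an inconsistency to be repaired, of minor to moderate severity. Followed strictly, 6.a is clean and the 8.c release does not touch the primary result; the documents do not support a claim that the primary accuracy is biased. Followed literally, 7.d.4 with 7.e.4 gives a different, wider reference that can include urine. In that case planned urine accuracy of 60% and 95% would read as 66.7% and 100%.

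Secondary objective 1 is not executable as written for unconfirmed children, and fewer than two rifampicin-resistant children are expected even among the 64 confirmed.

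For a TB-detection composite, the direction of the bias is clear but its size is not known from the documents. With p between 5% and 20%, specificity shifts by 0 to about 2.4 points at f = 0.5. In the cases tabulated with a non-zero shift, that is less than the sampling half-width, so it would not show in the results. All of this rests on the planning values and on assumed U, p and f; conversion on repeat testing would lower it.

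**What to change.** 1. In 7.d.4, 7.e.4 and section 10, state that the primary 2×2 table is built from the specimen-level lab CRF under 6.a, and that stool Xpert, urine Xpert and urine LAM do not count toward the reference. Report culture-positive or LAM-positive children who are negative under 6.a separately.
2. In 6.b, restrict the rifampicin analysis to children with a reference rifampicin result, and state whether the composite is also meant for TB detection.
3. If it is, identify the stool- or urine-positive, reference-negative, treated children and report the composite with them counted as TB and as not TB, as bounds. Children whose treatment began before the index test was run were not treated because of it; keep them as TB in both bounds.

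The test results and dates, treatment start and treatment date are already collected, so the cost is wording plus, if the composite is used, one extra table. Reported accuracy may be slightly less favourable, and some true TB found only by stool or urine will count as false positive in one bound. Release of results for care and the sample size of 327 are unchanged.
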